Main Inclusion Criteria	Adult patients undergoing general anaesthesia for relevant procedures during the pre-defined study window (as defined by this study, see Section 7) within hospitals affiliated with the Pan-London Perioperative Audit and Research Network (PLAN) and other regional trainee networks
Data collected/storage (if applicable)	Anonymised data will be stored on the PLAN REDCap secure data capture server.

4 Introduction

Although most airway management is uncomplicated, when complications occur they can be catastrophic resulting in significant morbidity and mortality [1]. The severe acute respiratory syndrome coronavirus-2 (SARS-CoV-2) pandemic has resulted in significant changes to airway management [2] due to concern over transmission of aerosolised virus particles to healthcare professionals [3]. Initial reports suggest that patients infected with SARS-CoV-2 may be more at risk of airway complications including hypoxaemia [4], airway trauma [5], and airway oedema [6]. While it is possible SARS-CoV-2 itself may be a risk factor for airway complications, aerosol precautions, designed to reduce the transmission of virus particles to healthcare workers, may also contribute. These aerosol precautions include modified anaesthetic techniques, unfamiliar equipment, and personal protective equipment (PPE).

Anaesthetic management varies, in part, depending on the patient's coronavirus disease 2019 (COVID-19) status. Personal protective equipment for droplet precautions is advised for staff dealing with COVID-19 negative patients and comprises eye protection, gloves, and surgical facemasks at the minimum [7]. COVID-19 positive or COVID-19 unknown patients require staff to use a greater level of aerosol precaution PPE, comprising respirator masks (e.g. FFP3), long-sleeved gowns, gloves and eye protection. It is currently not known whether use of aerosol precaution PPE and other methods used to reduce viral transmission during airway interventions increases the risk of airway complications, but it may be a contributing factor to difficult intubations reported in COVID-19 patients [6, 8].

We aim to describe airway management and the different components of the bundle of aerosol precautions used to protect healthcare workers, and report the associated incidence of airway complications.

5 Trial objectives and purpose

Aims

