- 1. To determine the incidence of airway complications in patients undergoing general anaesthesia during the COVID-19 pandemic.
- 2. To identify components of the aerosol precaution bundle (including PPE and anaesthetic techniques) which may be associated with a greater risk of airway complications.

6 Study design & Flowchart

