6.1 Study Design

AeroComp is service evaluation exploring the incidence of airway complications amongst patients undergoing general anaesthesia for surgical procedures within NHS Trusts. All adult patients undergoing any surgical procedure (with the exception of obstetric procedures) with the primary method of anaesthesia planned to be general anaesthesia will be eligible for enrolment to this study. The study duration will encompass 5 days (patients being enrolled over a 96 hour consecutive window with a further day of follow-up data collection) with an estimated total of 3600 patients being included. Individual sites are free to choose their own data collection window between 1st November

2021 and 3rd December 2021 as long as the 96 hour window commences at 07:30 on a Monday and closes at 07:29 on a Friday.

Primary outcome:

 Incidence of airway complications at both induction and emergence, defined as a composite of: airway trauma, aspiration, dental/lip/mucosal injury, change of intubation device, desaturation, three or more laryngoscopy attempts, grade 3 or 4 laryngoscopy, difficult face mask ventilation, difficult supraglottic airway device (SAD) usage, emergency front-of-neck airway, failed tracheal intubation, laryngospasm, oesophageal intubation (immediate or delayed recognition), requirement of reintubation immediately after extubation, and need for second intubator.

Secondary outcomes:

- Risk of composite outcome of airway complications will be reported for each individual component of the aerosol precaution bundle.
- Individual complications that comprise the primary outcome.
- Subjective operator assessment of airway difficulty
- Unanticipated airway difficulties necessitating significant deviation from the original airway plan.
- Composite risk of airway complication and association with confirmed/suspected COVID-19 infection, known negative COVID-19 infection without any potential COVID-19 risks, and all other patients.

7 List selection

Operating lists from all participating NHS hospitals will be included, with patients from those lists being eligible. Both elective and emergency cases will be included. The centres and local investigators will be identified by the Pan-London Perioperative Audit and Research Network (PLAN) or other national trainee research networks.

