Additionally, the lead for each site will submit, via the on-line REDCap system, the study week that site has selected (from one of weeks commencing 1st, 8th, 15th, 22nd or 29th November), the total number of eligible procedures for each 24 hour period of the study, and the list of all local investigators involved in the study (to enable production of certificates to demonstrate involvement as well as to allow naming of all collaborators on any manuscripts arising from the study). The site details data capture form is provided in *Appendix 3*.

All investigators and any other individuals contributing to the study will be required to comply with the Data Protection Act 2018 and the NHS code of confidentiality.

Data to be collected:

- Site (automatically populated dependent upon the login credentials of the local investigator)
- Day of the study
- Age of patient (grouped into 18-39, 40-59, 60-79 and \geq 80 years)
- Sex of patient
- American Society of Anesthesiologists (ASA) physical status
- Patient body mass index (BMI), grouped into underweight (< 18.5 kg/m²), normal (18.5 24.9 kg/m²), overweight (25.0 29.9 kg/m²), class 1 obesity (30.0 34.9 kg/m²), class 2 obesity (35.0 39.9 kg/m²), class 3 obesity (>= 40.0 kg/m²)
- Surgical urgency (elective; expedited; urgent; emergency)
- Start time of procedure (first set of observations entered into the anaesthetic record), grouped into daytime (07:30–17:59); evening (18:00–23:59); and overnight (00:00–07:29)
- Surgical specialty
- Surgical severity (minor; intermediate; major)
- Location of procedure: within or outside the main operating theatre complex (including stand-alone day surgery units), used to identify "remote-site anaesthesia".
- Grade of anaesthetist managing airway (initial airway manager and second airway manager if required)
- PPE worn by anaesthetist managing airway:
 - Eye protection: visor; goggles; other

- Respiratory protection: surgical mask; disposable FFP2/3 mask; re-usable FFP2/3 mask; powered air-purifying respirator; other

- Body protection: plastic apron; long-sleeved gown; hazmat suit; other
- Gloves: single pair; double pair; other
- Airway management technique- pre-oxygenation, mask ventilation, apnoeic oxygenation
- Airway equipment utilised to maintain oxygenation and facilitate anaesthesia, divided into:

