10.2 Statistical analysis

Incidence of airway complications amongst the sampled population will be reported as a composite of airway complications as mentioned in **Section 9**.

Continuous data will be reported using means (standard deviation, SD) or medians (interquartile ranges [range]) where appropriate. Categorical data will be reported as numbers (percentages, %) with 95% confidence intervals (CI) calculated using an appropriate method, where applicable. A p value of < 0.05 will be considered as statistically significant. Relationships between categorical variables and outcome measures will be presented as univariate odds ratios with accompanying p-values (Pearson's Chi-square test with Yates' continuity correction). Univariable logistic regression models will be fitted to investigate potential associations between variables describing patient, operator or procedural characteristics and the primary outcome of incidence of airway complications. A multivariable logistic regression model will then be fitted to include all covariates to obtain adjusted association estimates. Variables included in the regression modelling will be selected based on scientific and clinical plausibility of affecting the outcome of airway management.

11 Ethical considerations

This study is designed as a service evaluation, and no ethical approval is expected to be required. As we are collecting routinely captured data with no patient identifiable data, and will not involve either direct patient contact or influence their care in any way, no patient consent will be required. Approval from the Caldicott Guardian at the lead site (Guy's and St. Thomas' NHS Foundation Trust, London, UK), and audit registration at all recruiting centres will be required prior to commencing the project. Participating hospitals will ensure that their local investigators will be appropriately trained, but no GCP certification will be required from investigating teams as this is a service evaluation. The local PI will ensure that no patient identifiable information will be stored during the study.

12 Financing and Insurance

No funding will be required for this study. All investigators will be NHS employees working in their respective trusts and standard NHS Indemnity will apply.

13 Reporting and dissemination

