15.2 Appendix 2 – Sample Case Record Form (CRF)

AER	COMP	Study Day ¹ : D Monda	, ,	Study ID: Hospital	:	
PATIENT DETAILS		PATIENT COVID-19 STATUS		SURGICAL DETAILS		
Age: 18 to 60 to Sex: Male Fema Other	79 🗖 80 and over	 Positive (PCR/LFT positive; CC Negative (PCR/LFT negative a COVID-19 free pathway) 	WID-19 symptoms; recent exposure) nd self-isolated and cohorted in	Surgical urgency ² :	Severity ³ : D Mind D Inter D Majo	rmediate
ASA Score:	− 29.9 □ 30.0 − 34.9	Unclear (No test result availal isolated; not cohorted in COVID-		Specialty: Breast ENT Bariatric General Cardiac Gynaecology Cardiology Max-Fax Dental Neurosurgery Other:	 Ophthalmology Ortho/Trauma Plastics Radiology Thoracic 	TransplantUrologyVascular
ANAESTHETIC DETA				Procedure performed within main operating theat	re complex: D Yes	No
Start time ^{1,4} : Grade of initial airway manager ⁵ : PPE worn by anaest Eye protection:	 00:00 to 07:29 07:30 tilde CT1-2 ST5-7 Consultion CT/ST3-4 SAS/SCF Other Other 07:30 tilde 07:30 ti	Itant Grade of second her airway manager ^{5,6} :	5 B	AIRWAY COMPLICATIONS (tick all that apply) Tracheal intubation attempts ⁸ : 1 2 Best grade of laryngoscopy ⁸ : 1 2 Was the patient woken up at the end of surgery? ⁹	□ 3 □ >3 □ 2b □ 3 □ Yes □ No	□ 4
Respiratory	 Other Surgical face mask 		Hazmat suitOther	Airway complications: (tick all that apply)	Induction	Emergence ⁹
rotection:	 Disposable FFP2/3 respirator Re-usable FFP2/3 respirator Powered air purifying respira Other 		 Single pair of gloves Double pair of gloves Other 	Airway trauma Aspiration Change of intubation device Death ¹⁰		
IRWAY MANAGEN Induction:	MENT (tick all that apply) Inhalational Intravenous: non-RSI	Equipment:	Bougie Stylet Cofeed pillour	Dental injury Desaturation (SpO₂ ≤90%) Desaturation (SpO₂ ≤80%) Difficult mask ventilation (2-person technique)		
Dxygenation:	 Intravenous: RSI/modified RS Pre-oxygenation Post-induction mask ventilati Apnoeic oxygenation 	ion	 Oxford pillow High-flow nasal cannulae Low-flow nasal cannulae Clear plastic 'aerosol' box Other 	Difficult SAD (excessive leak, poor ventilation, hypo Emergency front-of-neck airway Failed tracheal intubation – continue with SAD		
Airway device:	 Face mask (as sole airway de Supraglottic airway device Tracheal tube Other⁷ 	Airway technique: Direct laryngoscopy Video laryngoscopy Flexible bronchosco		Failed tracheal intubation – awaken patient Laryngospasm not reversed with positive pressure Lip/mucosal injury	D	

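### The case record form's single mask-ventilation tick does not separate ventilation that was part of the initial technique from ventilation given in response to a complication, which biases its association with the composite outcome

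*Protocol*

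**What the plan says.** Aim 2 in Section 5 of the Protocol is "To identify components of the aerosol precaution bundle (including PPE and anaesthetic techniques) which may be associated with a greater risk of airway complications". The first secondary outcome in Section 6.1 carries this through: "Risk of composite outcome of airway complications will be reported for each individual component of the aerosol precaution bundle". The Introduction describes the precautions by class only: "These aerosol precautions include modified anaesthetic techniques, unfamiliar equipment, and personal protective equipment (PPE"). No section lists the members of the bundle one by one.

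Mask ventilation is collected in two places. Section 9.1 lists it among the data items as "Airway management technique- pre-oxygenation, mask ventilation, apnoeic oxygenation". The CRF in Appendix 2 gives it one box, the second of three under oxygenation, "Pre-oxygenation Post-induction mask ventilati Apnoeic oxygenation" (the word is cut short in the text), in a panel where several boxes may be ticked. None of CRF notes 1-11 says whether the box means ventilation before the first airway attempt, planned ventilation, or any mask ventilation after induction.

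The composite in Section 6.1 includes desaturation, failed tracheal intubation, change of device and difficult mask ventilation. Section 10.2 states the analysis: "Relationships between categorical variables and outcome measures will be presented as univariate odds ratios", followed by univariable and multivariable logistic regression on the composite.

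**The concern.** An exposure should be fixed before the outcome occurs. Here a complication can set the exposure. Take a patient in whom mask ventilation was not part of the initial technique. If nothing goes wrong, the box stays empty. If the patient desaturates or an attempt fails and the mask is then used, the literal reading of the box is that it is ticked. The complicated case leaves the non-ventilated group and joins the ventilated group because it was complicated.

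The direction follows from the mechanism: the non-ventilated group loses events and the ventilated group gains them. Adjusting for patient, operator and procedural characteristics, as Section 10.2 intends, cannot restore the lost classification, because the error depends on the outcome itself.

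A second link acts the same way. Difficult mask ventilation is part of the composite and can occur only in patients who were mask ventilated.

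At stake is the component-level question in Aim 2 and the matching secondary outcome. A technique that raises risk could appear less harmful than it is, or neutral, or even protective.

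**Working it through.** **1. The plan's own figures.** Appendix 4: n = N·p(1−p) / [(d²/Z²)(N−1) + p(1−p)] with N = 1,000,000, p = 0.05, d = 0.01, Z = 1.96 and design effect 1 gives 1821.4, rounded up to 1822, as stated. Section 10.1: 50 centres × 18 procedures × 4 days = 3600, as stated. Neither figure concerns the mask-ventilation contrast, and neither is affected.

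**2. Inputs for the bias.** From the Protocol: 3600 patients and a composite incidence of about 5%. Not in the Protocol, so assumed: the share not initially ventilated (f), the risk in each group, and the share r of complicated, initially non-ventilated cases that then receive mask ventilation and are ticked.

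**3. Base case.** f = 20%, risk 8% when not initially ventilated and 4.5% otherwise. The overall risk is 0.2 × 8% + 0.8 × 4.5% = 5.2%, close to the planning value.

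- Not initially ventilated: 720 patients, a = 57.6 events, b = 662.4 without.
- Ventilated: 2880 patients, c = 129.6 events, d = 2750.4 without.
- True OR = (57.6/662.4) / (129.6/2750.4) = 1.85.

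Moving a share r of a across gives observed OR = [a(1−r)/b] / [(c + r·a)/d]:

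| r | Not ticked: events/no events | Ticked: events/no events | Observed OR |
|---|---|---|---|
| 10% | 51.84/662.4 | 135.36/2750.4 | 1.59 |
| 25% | 43.2/662.4 | 144.0/2750.4 | 1.25 |
| 50% | 28.8/662.4 | 158.4/2750.4 | 0.75 |
| 75% | 14.4/662.4 | 172.8/2750.4 | 0.35 |

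**4. Where the sign reverses.** Setting the observed OR to 1 gives r* = (ad − bc) / [a(b + d)] = (158,423.04 − 85,847.04) / (57.6 × 3412.8) = 72,576 / 196,577.28 = 0.369, about 37%.

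**5. Sensitivity to f (same risks, r = 50%).**

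- f = 10%: (14.4/331.2) / (160.2/3094.2) = 0.84.
- f = 40%: (57.6/1324.8) / (154.8/2062.8) = 0.58.

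**6. No true effect (5% v 5%, f = 20%, r = 50%).** (18/684) / (162/2736) = 0.44. With no true effect, any r above zero gives an observed OR below 1.

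**7. Other true effects.** With 5% risk in the ventilated group and f between 50% and 10%, the sign reverses only when r exceeds 9-16% (true risk 6%), 18-32% (7.5%) or 27-48% (10%). Below those values the harm is diluted but still visible.

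**8. How the form treats comparable items.** CRF note 7 confines the 'Other' airway device tick to the primary device after induction. Section 9.1 counts a bougie as a change of device only when its use was not foreseen. The mask-ventilation tick has no such limit.

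**The case against.** Five points can fairly be made on the other side.

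- **Withholding mask ventilation is not named as a precaution.** This is correct. A reader might infer that the absence of a tick is the declared exposure for Aim 2, but the Protocol names no such contrast, and Section 9.1 is a general data list not tied to that aim. The contrast is only implied by the reference to anaesthetic techniques. It remains a natural use of the item, because Aim 2 covers techniques and Section 9.1 files mask ventilation under airway management technique.
- **The form does not say that rescue ventilation counts.** This is also correct. The box follows the induction item and sits among routine oxygenation steps, while problems have their own panel. Some anaesthetists will read it as the routine step before the airway device. Nothing tells them to, and mixed readings across about 50 centres would leave part of the bias.
- **The rescue share may be small.** The composite also covers emergence and includes dental, lip and mucosal injury, grade 3 or 4 views and reintubation after extubation. Many of these need not prompt mask ventilation after induction, so high values of r are not supported by the document. This stands, and it is why no single size can be claimed.
- **Other fields help.** The induction item (RSI/modified RSI or not) and the deviation-from-plan item allow a partial sensitivity analysis. Neither records whether mask ventilation was part of the initial technique, and a deviation may itself follow a complication.
- **The study is descriptive and the primary outcome is untouched.** This is true, and it limits the weight of the point.

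**Conclusion.** The point holds as a recording ambiguity that biases one exposure in the component-level analysis. If ventilation given in response to a complication is ticked, as the literal wording allows, the bias runs towards making no mask ventilation look safer, and adjustment for baseline characteristics cannot remove it.

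The size is unknown because the Protocol gives neither the share not initially ventilated nor the rescue share. In the base case a true odds ratio of 1.85 is diluted to 1.59 at 10% rescue and 1.25 at 25%. It reverses only above about 37%. A reader might infer that the technique will come out as protective. The document does not support that as a general statement: where there is true harm, a reversal needs a rescue share that nobody has stated.

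The primary incidence estimate, the 1822 and the 3600 are unaffected. The change is worth making before collection starts. Under Section 9.1 the local ID is detached once the CRF is complete and is not uploaded, so intent and timing could not reliably be recovered from the notes afterwards.

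**What to change.** Replace the single box, on paper and in REDCap, with a three-option field on mask ventilation after induction:

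1. given before the first airway device attempt as part of the initial technique;
2. not given;
3. given only in response to a complication.

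Analyse by initial technique: option 1 against options 2 and 3 together.

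If the layout cannot change, add a CRF note in the style of note 7. It should say that the box is ticked only for mask ventilation before the first airway device attempt and not in response to a complication.

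Neither change removes the link through difficult mask ventilation, so also report this association with that component left out of the composite.

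If data have already been collected on the current form, state the limitation, give its direction, and use the induction type and deviation-from-plan items for a sensitivity analysis, described as partial.

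The cost is at most one extra tick per case and one extra sensitivity analysis. It changes recording only, and needs no extra patients or procedures.

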 - Airway devices utilised: facemask, supraglottic airway device; tracheal tube; other (including rigid bronchoscope, jet ventilator and transnasal humidified rapid-insufflation ventilatory exchange)
 - Airway techniques including: direct laryngoscopy; videolaryngoscopy; use of a flexible bronchoscope over which a tracheal tube is passed, categorised into whether performed awake or asleep
 - Use of cricoid force?

- Adjunct equipment including: bougie; stylet; Oxford or HELP pillow; high and lowflow nasal cannulae; aerosol boxes or drapes; as well as a free text option for other potential equipment

- Patient COVID-19 status:
 - Positive: RT-PCR or lateral flow test positive for SARS-CoV-2; OR symptoms consistent with COVID-19 with no SARS-CoV-2 test available; OR recent exposure to SARS-CoV-2
 - Negative: RT-PCR or lateral flow test negative for SARS-CoV-2 infection; AND actively cohorted with other COVID-19 negative patients for the entirety of their hospital stay prior to this operation; AND self-isolated according to institutional guidelines.
 - Unclear: No SARS-CoV-2 result available with no risk factors; OR not self-isolated according to institutional guidelines; OR not in a COVID-19-free pathway.
- Whether anaesthesia was terminated at the end of the procedure with a plan to wake up the patient (emergence from anaesthesia).

Airway complications:

- Number of tracheal intubation attempts.
 An attempt is defined by the number of times the laryngoscopy device is inserted or reinserted into the patient's airway.
- Best grade of laryngoscopy: modified Cormack and Lehane grading [9] into 1, 2a, 2b, 3 and 4.
- The following complications categorised into induction and emergence (defined as the period around the time of cessation of anaesthesia until hand over of patient to recovery/intensive care staff):
 - Airway trauma: evidence of airway bleeding or oedema.
 - Dental injury (arising solely from anaesthetic, rather than surgical, interventions)
 - Lip and mucosal injuries (arising solely from anaesthetic, rather than surgical, interventions)
 - Pulmonary aspiration: inhalation of oropharyngeal or gastric contents into the larynx and lower respiratory tract [10]
 - Change of intubation device: use of an additional airway device, e.g. change from supraglottic airway to tracheal tube, change from direct to videolaryngoscopy (or vice versa), use of bougie if not initially anticipated, change in type of laryngoscope e.g. McCoy vs Macintosh blade

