 - Desaturation: reduction in oxygen saturations to ≤90% during airway management
 - Severe Desaturation: reduction in oxygen saturations to ≤80% during airway management
 - Difficult mask ventilation: need for two-person (or more) mask ventilation
 - Difficult SAD insertion: multiple insertion attempts; excessive leak; insufficient ventilation; change of SAD size/design

- Failed tracheal intubation even after intervention of a second airway manager, including:

- If oxygenation and provision of anaesthesia was possible via SAD and a decision was made to continue with surgery

- If a decision was made to wake the patient and abandon surgery
- If this resulted in death this should be recorded separately, as above
- Laryngospasm: unwanted muscular response of the larynx that produces partial or complete obstruction of the laryngeal airway [11].
- Oesophageal intubation (recognised): tracheal tube placed in the oesophagus and recognised before delivery of the fourth ventilatory breath
- Oesophageal intubation (delayed recognition): tracheal tube placed in the oesophagus and 4 or more ventilatory breaths delivered.
- Reintubation within 30 minutes of the end of the procedure
- Second airway manager: initial airway manager either requests the assistance of a second individual to directly manage the airway or the supervising anaesthetist requests a second individual to take over management of the airway.
- Emergency front-of-neck airway
- Death due to hypoxia or other complication of airway management.
- Significant deviation from original airway plan
- Subjective assessment of ease of 1) mask ventilation, 2) SAD placement and use, and
 3) tracheal intubation, using a 5-point Likert scale (1-5) with addition of "not attempted" for each question

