- 6) Second airway manager: if a second individual took over management of the airway following management by the initial airway manager their grade should be recorded here and "second airway manager required" ticked within the complication section. Leave blank if not applicable.
- 7) Other: this applies to, for example, rigid bronchoscopes, jet ventilators and transnasal humidified rapid-insufflation ventilatory exchange. This should be ticked only if it was the primary airway device following induction of anaesthesia. Typically this will be a planned technique involving pre- +/- per-oxygenation following discussion with the operating surgeon beforehand. Also select if the primary means of oxygenation during the procedure is via a surgically placed jet ventilator (e.g. laryngeal procedures) and no other airway device is placed prior or subsequently by the anaesthetist. The exact device used does not have to be specified.
- 8) Tracheal intubation attempts/laryngoscopy grade should be left blank if intubation is not attempted. The grade here refers to the Cormack and Lehane system as modified by Yentis and Lee, shown below.
- 9) If the patient was not woken up at the end of surgery, emergence complications should not be recorded. If the patient was woken up and then immediately reintubated, this should be recorded as: Woken up: Yes; Reintubation immediately post-procedure: On emergence.
- 10) Only death due to hypoxia or another complication of airway management should be recorded.
- 11) Recognised oesophageal intubation is detected after the first but before the fourth ventilatory breath has been delivered. Delayed recognition is when four or more ventilatory breaths have been delivered.

	1	2		3	
Original Cormack and Lehane system	Full view of the glottis	Partial view of the glottis or arytenoids		Only epiglottis visible	Neither glottis nor epiglottis visible
View at laryngoscopy	E	Y	Y		
Modified system	1 As for original Cormack and Lehane above	2a Partial view of the glottis	2b Arytenoids or posterior part of the vocal cords only just visible	3 As for original Cormack and Lehane above	4 As for original Cormack and Lehane above

E = epiglottis, LI = laryngeal inlet. From Yentis SM, Lee DJH. (1998) Grading of direct laryngoscopy. Anesthesia. 53:1041-4.

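### The case record form does not record the composite that Section 10.2 takes from Section 9: laryngospasm is narrowed, and the reintubation and second-manager rules disagree

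*Protocol*

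**What the plan says.** Protocol Section 10.2 states that the incidence will be "reported as a composite of airway complications as mentioned in" Section 9. The definitions in Section 9.1 therefore govern the analysis, alongside the list under the primary outcome in Section 6.1.

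- **Laryngospasm.** Section 6.1 lists it without qualification. Section 9.1 defines it as "Laryngospasm: unwanted muscular response of the larynx that produces partial or complete obstruction of the laryngeal airway". The box on CRF v1.2 in Appendix 2 reads "Laryngospasm not reversed with positive pressure".
- **Reintubation.** Section 6.1 has "requirement of reintubation immediately after extubation"; Section 9.1 has "Reintubation within 30 minutes of the end of the procedure". The CRF item asks about reintubation straight after the procedure, and note 9 describes a patient who is woken and then reintubated at once. Section 9.1 also ends the emergence period at handover: it runs "until hand over of patient to recovery/intensive care staff".
- **Second airway manager.** In Section 9.1 the item is met when the "initial airway manager either requests the assistance of a second individual to directly manage the airway", or when the supervisor requests a second individual to take over. CRF note 6 tells staff to tick the item "if a second individual took over management of the airway following management by the initial airway manager".

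**The concern.** Under Section 9.1, the anaesthetist or anaesthetic assistant completes the CRF. What reaches the database is what the form asks for, not what the protocol text defines. If the form is narrower than Section 9.1, the reported incidence does not match its published definition.

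Two results are exposed. The first is the primary composite. The second is the set of individual complications, a secondary outcome, where a lost laryngospasm is a direct loss because no other component can stand in for it.

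The loss would be hard to repair later. The local ID is detached once the form is complete and is never uploaded, and cross-checking against notes is asked for only where appropriate. An episode that the form told staff not to tick cannot readily be recovered.

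**Working it through.** **1. Definitions side by side**

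| Component | Section 6.1 | Section 9.1 | CRF v1.2 and notes |
|---|---|---|---|
| Laryngospasm | Unqualified | Any, partial or complete | Only if positive pressure did not reverse it |
| Reintubation | Immediate | Up to 30 minutes after the procedure | Immediate (item and note 9) |
| Second manager | Need for one | A request for direct airway help or for take-over | A take-over happened (note 6) |

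*Laryngospasm.* The CRF adds a condition on response to treatment that appears nowhere in the body text. The form shows no second laryngospasm box, and none of its notes restores the wider definition. A reversed episode meets Sections 6.1 and 9.1 but has no place on the form.

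*Reintubation.* The CRF and Section 6.1 agree in substance; Section 9.1 stands apart. A reintubation in recovery at 20 minutes meets the Section 9.1 item, but falls outside the emergence period in the same section and outside the CRF wording.

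*Second manager.* A request that did not end in a take-over meets Section 9.1 but not note 6.

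**2. The plan's own figure**

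Appendix 4 uses p = 0.05, d = 0.01, N = 1,000,000, design effect 1 and Z = 1.96:

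n = N·p(1−p) / [(d²/Z²)(N−1) + p(1−p)] = 47,500 / (26.032 + 0.0475) = 1821.4, rounded up to 1822.

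This reproduces the stated number. The expected 3600 is 50 centres × 18 procedures × 4 days. At 3600 and 5%, the 95% half-width is 1.96 × √(0.05 × 0.95 / 3600) = 0.0071, or ±0.71 points.

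**3. Upper bound for laryngospasm**

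Let r be the laryngospasm rate, s the share reversed with positive pressure, and u the share of reversed episodes in patients with no other qualifying event. The loss from the composite is r × s × u, which is at most r × s. The protocol gives none of the three. Assuming r = 1% and s = 50 to 90%:

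- bound: 1% × 0.5 = 0.5 points to 1% × 0.9 = 0.9 points;
- in 3600 patients: 18 to about 32;
- laryngospasm as an individual outcome would be recorded at 0.5% down to 0.1%, instead of 1%.

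**4. All three items together**

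Assume a true composite of 5%. Let 0.25 to 1.5% of patients have one of these three items as their only qualifying event, and let the form miss 25 to 75% of them.

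- Smallest loss: 0.25% × 0.25 = 0.06 points, measured 4.94%, about 2 patients in 3600.
- Largest loss: 1.5% × 0.75 = 1.13 points, measured 3.88%, about 41 patients in 3600.

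**5. Effect on the interval**

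For a bias b at n = 3600, coverage of the true 5% is Φ(1.96 − b/SE) − Φ(−1.96 − b/SE), with SE = √[(0.05 − b)(0.95 + b)/3600].

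- b = 0.25 points: SE = 0.355 points, coverage about 89%.
- b = 0.5 points: SE = 0.346 points, coverage about 70%.

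**The case against.** The strongest reply is that only one of the three mismatches is clear-cut, and that the size is entirely assumed. Much of that is right.

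- **Reintubation.** A reader might infer that the CRF departs from both Sections 6.1 and 9.1 on every item. For reintubation it does not: it matches Section 6.1 in substance, so the fault is mainly a contradiction within the body text. The Section 9.1 item also carries its own window, and the protocol allows a further day of follow-up data collection. The contradiction remains, because Section 10.2 points to Section 9.
- **Second manager.** Both limbs in Section 9.1 concern a second person handling the airway, which is close to a take-over. The remaining gap is narrow. A reader might also infer that note 6 sweeps in planned training handovers, inflates the composite and biases the association with operator grade. The documents do not support this. They mention no such handovers, the box says the second manager was required, note 6 says to leave the grade blank if not applicable, and the supervisor limb of Section 9.1 would not exclude them either.
- **Size.** A reader might take 0.5 to 0.9 points as the loss from the composite and conclude that it uses up nearly all of the ±1 point precision. It is an upper bound on assumed rates. A patient who also desaturated, needed two-person mask ventilation or had a change of device still counts.

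The laryngospasm row may continue beyond the words legible in the text at hand, so it should be checked on the form itself. The restriction to non-reversed episodes is legible, and this part of the concern stands.

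**Conclusion.** The concern holds, chiefly for laryngospasm. The current form leaves out reversed episodes that Sections 6.1 and 9.1 both count, so the laryngospasm rate and the composite are under-counted against the definition that Section 10.2 adopts. Reintubation is a real but different fault: two sections contradict each other, and the form misses later events that Section 9.1 counts. The second-manager gap is minor.

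The direction supported by the documents is under-counting. The amount cannot be determined from them: the bound in step 3 and the ranges in steps 4 and 5 rest on assumed rates and show only that the effect could run from negligible to about the size of the planned precision. The definitional conflict does not depend on those figures. Nothing here disputes the sample size calculation, and aligning the definitions leaves it at 1822.

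**What to change.** Settle these points before the data collection window opens on 1 November 2021.

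1. **Laryngospasm.** Make the box on the CRF and e-CRF cover any laryngospasm, partial or complete. If severity is wanted, add an optional sub-tick for episodes that positive pressure did not reverse.
2. **Reintubation.** Choose one window, use it in Section 6.1, Section 9.1, the CRF item and note 9, and make it consistent with the emergence recording period.
3. **Second manager.** Reword note 6 to the Section 9.1 rule, so that a request for direct airway help is ticked even if no take-over followed.

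Items 1 and 3 cost a few words on the form, its notes and the e-CRF. Item 2 also needs edits to the body text. If the window chosen runs past handover to recovery, it is more than an edit: someone must record events after the theatre team has left the patient. None of the three changes the sample size. If data have already been collected on v1.2, the report should define each component as the form recorded it and state how that differs from Section 9.1.
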